Because both the primary and secondary outcome measures are continuous, normally distributed measures, we anticipate having to rely on normal theory analytic methods. Specifically, mixed linear regressions on the primary (HEI) and secondary outcome measures (such as Fruits & Vegetable subscores, BMI and parent HEI) will be fitted to test differential trajectories for two groups from baseline to midpoint and end point assessment of the program, time expressed as days elapsed from baseline. These models readily accommodate differential dropout in the arms with maximum likelihood estimation, random intercepts, and also adjust for any clustering effect of the BGCAA sites. Because randomization will be stratified by whether the family are SNAP recipients or not, the main effect of family's SNAP beneficiary status will be included in all models in addition to the main target terms of interest: two-way interactions of time X treatment, time X SNAP, and their three-way interaction. Overall alpha will be set at 0.05 for each child outcome on these target terms.

In addition to these intention-to-treat (ITT) analyses we will also conduct as-treated (AT) analyses incorporating the 'dose' variable that will be formed based on implementation database elements that permits the tracking of program elements consumed/ picked up/ attended by the target child and his/her parent/guardian in the two active arms. In AT models, total dose taken-up by the end of the program will enter into product terms with time. As is typical, we expect the AT models to have greater sensitivity/ precision in estimating the added value of the family support beyond the elements of the after-school program with CATCH for change in HEI and secondary outcomes. In addition the dose variable sheds light on the effects of Boys and Girls Club programming, including CATCH, regardless of other incentives. Statistical controls for family demographic characteristics, food insecurity, child age, sex, and SNAP beneficiary status will be included in the AT framework as 'dose' is not completely controlled by the randomization and hence would be expected to be correlated with these characteristics (e.g. economically disadvantaged families may be more likely to uptake more of the program elements).

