The greatest opportunity lies in exploratory analyses of the two randomized arm participants that permit the estimation of dose-response based on family characteristics. Both the "after-school program with CATCH" and the "after-school program with CATCH + family support" intervention arms are expected to show variation in dose. In the case of dose for "after-school program only"

participants, we expect dose variation to be predicted by structural characteristics of family routines (e.g. number of days the target child attends BCG after-school program is predicted by whether both parents are employed, family income, number of siblings and caretakers in the family as alternatives to BCG attendance). In contrast, dose for “after-school program with CATCH + family support” participants is more complex and includes distinct elements that require greater motivation on the part of the parent/ guardian to engage with (e.g. completing goal sheets and receiving incentives versus not completing incentivized elements of the program). We will model the associations of separate aspects of ‘dose’ with response (HEI, physical activity) and predict separate aspects of ‘dose’ from family characteristics at baseline. These exploratory analyses will provide clues on how to structure future programs, incentivize participation, as well as inform who is likely to benefit the most. In the exploratory analytic framework, we will engage in omnibus correction for inflations in type-I error rate and will not interpret any significant single result unless at least 10% of all examined associations are significant.

STUDY ELEMENT IDENTIFICATION

6 Study Elements

Check each research procedure included in your study.

A full description of all study procedures should be provided in the Procedures (Details) section below.

Procedures denoted with “” below have supplemental forms. Navigate to the [UTRMS-IRB Library, Templates](#) tab to download the applicable supplemental form.*

 Bio-specimens*	 Biometrics	 Registry or Repository*
 Focus Group	 Genetic Analysis	 Genomic Data Sharing
 International Research*	 Interview/Survey	 MRI

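### The exploratory dose models cannot show which families benefit most from family support; a few randomised treatment-by-characteristic terms could address this, though imprecisely

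*Combined protocol and SAP*

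**What the plan says.** The exploratory part of section 5 (Data Analysis) presents the two randomised arms as offering analyses "that permit the estimation of dose-response based on family characteristics". It then names two models:

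- **Dose with response:** "We will model the associations of separate aspects of ‘dose’ with response (HEI, physical activity").
- **Family characteristics with dose:** the analysts will "predict separate aspects of ‘dose’ from family characteristics at baseline".

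The results are meant to help shape later programs and incentives, "as well as inform who is likely to benefit the most".

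The same section says that support dose "includes distinct elements that require greater motivation on the part of the parent/ guardian to engage with". In describing the as-treated models it says that dose "is not completely controlled by the randomization and hence would be expected to be correlated with these characteristics". Those models adjust for family demographics, food insecurity, child age and sex, and SNAP status.

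The only place where the randomised effect may vary with a baseline characteristic is the intention-to-treat model, whose target terms are "two-way interactions of time X treatment, time X SNAP, and their three-way interaction".

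The exploratory analyses carry an omnibus type I error correction. No single significant result is to be interpreted unless a tenth or more of the associations tested are significant.

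**The concern.** Benefit for a type of family is the difference in outcome between families of that type who were offered support and families of that type who were not. Neither named model makes that comparison. The characteristic-to-dose model describes uptake. The dose-to-response model describes whether families with higher uptake change more, and motivated caregivers may both take up more and improve their child's diet more for other reasons. Joining the two models does not yield benefit by family type.

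At stake is advice on whom later programs should target. That advice would rest on self-selected uptake, although the trial has a 1:1 randomised control arm with the same baseline data.

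**Working it through.** **1. The plan's own figure for the dose analyses.** Section 15 (Sample size rationale) gives r = 0.31, 80% power and total N = 79. With Fisher's z and two-sided alpha 0.05 (sidedness is not stated, so two-sided is assumed), N = ((1.960 + 0.842)/atanh(0.31))² + 3 = 79.4. At N = 79 the power is 79.8%, so the figure reproduces. It concerns detecting an association; it does not bear on whether the association measures benefit.

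**2. What each model estimates.**

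| Analysis in section 5 | Quantity estimated | Randomised comparison within a family type? |
|---|---|---|
| Dose with response | Change by level of uptake | No |
| Family characteristics with dose | Uptake by family type | No |
| Time x treatment x SNAP | Arm difference in change, by SNAP status | Yes |

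The baseline descriptor table in section 4 (Design and Methodology) lists household income, the USDA 6-item food security tool, and the child's sex and date of birth. Data for further terms of the third kind are therefore already collected. The measurement tables in section 4 contain no measure of caregiver motivation.

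**3. Whether the dose models could point to the wrong families.** This is a large simulation with assumed values, not values from the plan. A binary characteristic raises mean dose from 0.50 to 0.71, motivation raises both dose and diet change, and the effect of being offered support is set separately for each group.

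| Quantity | Equal true benefit | Low-uptake group benefits more |
|---|---|---|
| True effect, low-uptake / high-uptake group | 0.47 / 0.47 | 0.77 / 0.17 |
| Mean dose, low-uptake / high-uptake group | 0.50 / 0.71 | 0.50 / 0.71 |
| Dose-response correlation, intervention arm | 0.33 | 0.17 |
| Arm difference within group | 0.47 / 0.47 | 0.77 / 0.17 |

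In the second case the uptake model favours the group that benefits less, and the dose-response correlation is still positive. Only the arm difference within each group recovers the truth. The simulation shows that this can happen, not how likely it is here.

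**4. Confounding of dose-response alone.** Suppose support has no effect and motivation correlates r with both uptake and diet improvement. Dose and response then correlate r²: 0.09, 0.16 and 0.25 for r = 0.3, 0.4 and 0.5. Among 96 intervention children (the retained number in one scenario of section 15), an uncorrected two-sided 5% test is significant in about 14%, 34% and 70% of trials. These are within-arm figures under assumed correlations. They contain no family characteristic and do not apply the plan's multiplicity rules.

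**5. Precision of the randomised alternative.** For a binary characteristic with prevalence p, the standard error of the difference between the two arm differences is the main-effect standard error divided by √(p(1−p)), that is, twice as large at p = 0.5. The main-effect standard error is taken either without clustering, √(2/n), or as implied by the plan's detectable effects, d/2.80. The detectable interaction with 80% power at p = 0.5 is then:

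| Retained per arm | Unclustered: 2.80 x √(2/n) x 2 | Plan-implied: 2 x d |
|---|---|---|
| 120 | 0.72 SD | 2 x 0.47 = 0.94 SD |
| 96 | 0.81 SD | 2 x 0.49 = 0.98 SD |
| 64 | 0.99 SD | 2 x 0.60 = 1.20 SD |

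At an assumed prevalence of 30%, the range at 120 per arm is 0.79 to 1.03 SD. Power for an interaction of 0.47 SD (50% prevalence) is 44% to 29% at 120 per arm and 26% to 19% at 64 per arm. The plan gives no cluster size, so its 120 per arm cannot be rebuilt (72 per arm suffices for d = 0.47 without clustering). The two columns therefore serve as a bracket.

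**The case against.** The strongest reply is that these analyses are labelled exploratory, are said to offer only clues, and carry both an omnibus correction and the 10% rule. That stands as a limit on the seriousness of the point. It does not answer the point, because those rules deal with chance, whereas shared motivation pushes many dose associations the same way and makes the 10% threshold easier to pass.

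A second reply is that the phrase "permit the estimation of dose-response based on family characteristics" may mean a dose x characteristic term. That reading is possible, but no such term is specified, and it would still compare families by self-selected uptake.

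A third is that the randomised terms would be weak. This is correct, as the table shows: several such terms would seldom separate real moderators from chance. They would nevertheless give unconfounded estimates of the quantity in question, and more data would not remove the confounding from the dose models.

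A reader might infer more than the documents support:

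- **That the plan will name high-uptake families as those who benefit most.** It contains no such rule.
- **That the dose models show only engagement.** This fits the characteristic-to-dose model; the other relates dose to outcome.
- **That the exploratory work ignores the randomised arms.** It is set among participants of both arms, and the plan does not say whether support-dose models pool them. If control children entered at zero dose, the null correlations in step 4 would fall to about 0.02 to 0.11 under assumed goal-sheet uptake (mean 2.5 to 3.5 of 5, SD 1.5 to 1.0).
- **That step 4 gives the plan's false-positive rates.** It does not. The correlations are assumed, and the plan links motivation to engagement, not explicitly to diet change.

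**Conclusion.** The point holds as a mismatch between an exploratory aim and the models named for it. Those models can describe engagement and a non-randomised dose-response relation; they cannot identify who benefits most. This conclusion rests on the plan's own statements about dose and motivation and on the absence of any randomised moderator other than SNAP. It does not depend on the simulated figures. The listed as-treated covariates do not include motivation, and whether they carry over to the exploratory models is not stated.

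The point is minor: the primary intention-to-treat analysis and the sample size are untouched. The randomised alternative is unconfounded but imprecise, with a detectable interaction of about 0.7 to 1.2 SD for 120 down to 64 per arm. That range assumes a binary characteristic at 50% prevalence, 80% power, two-sided 5% testing and a simple comparison of arm differences.

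**What to change.** In section 5, for the who-benefits question, add exploratory time x treatment x characteristic terms for a short prespecified list collected at baseline, for example food security, household income and child age or grade. Place them beside the existing SNAP term. Report arm differences by level of each characteristic with confidence intervals, and label them exploratory.

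Keep the dose models. State that they inform engagement and non-randomised dose-response, not who benefits most, and say whether support-dose models pool the arms and which covariates they include.

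The cost is a few extra models and a sentence or two, with no new data. The drawback is low precision, which the text should acknowledge. If the investigators prefer not to add terms, rewording the aim to refer to who is likely to engage would remove the mismatch, but would leave the who-benefits question unanswered beyond SNAP.

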Provide a brief description of the study design or data collection methodologies. Details regarding protocol specific research procedures will be discussed in a later section.

Design: A two-arm randomized trial.

Randomization:

- Eligible households with at least one child (reference child) in the BGCAA after-school program whose caregiver/parent (guardian) (reference caregiver) consents to participate in the study will be randomized to either the active intervention or the control (1:1 ratio). Randomization will be stratified by the family's SNAP beneficiary status as SNAP could affect uptake of treatment elements offered in the family support arm.

Blinding: Outcome assessors, principal investigator, and biostatistician are blinded to participant allocation. Participant and other staff are unblinded.

Study arms (19 weeks) (Figure 1):

Randomized arms

Children in both intervention and control arms participate in the BGCAA's after-school program with CATCH curriculum.

1. Across participating school sites, the whole BGCAA's after-school program runs for 3h, Mon-Fri for the school year. Children enrolled are expected to attend a minimum of 2x/week.
2. CATCH curriculum will be delivered as a component of the after-school program in blocks of 45-60 min, twice a week.
3. Children also participate in active recreational time (approx. 60 min, offered 1x/week at a minimum) which consists of a mixture of free play, structured physical activity games, and/or sports activities (including soccer, football, and basketball).

Intervention arm: BGCAA after-school program + Family support

1. Children participate in the BGCAA's after-school program with CATCH curriculum as described above.
2. The child's caregiver will receive the following:
 - Family tip sheets sent via mobile text at the start of the program and then every 3 weeks, to a total of 6 txt messages.
 - Weeks 1-4 (4 weeks):
 - i. Welcome package mailed to the family's residence approximately in the first week of the program.

- ii. Weekly: 1 box of produce
- iii. Recipes accompanying each box (sample recipe card attached to submission)
- iv. Bi-Weekly: Grocery store gift cards (2x \$20, to a total of \$40)
- Weeks 5-19 (total of 10 weeks over the 19-week study timeline):

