 - i. For five weeks, an optional online form (or “*goal sheet*”) will be sent to the parent/caregiver (5 sheets in total) with questions about trying new FV items to be completed within the next 7 days. As an incentive, a \$10 gift card will be sent the following week to those who complete it (a potential total of \$50).
 - ii. Week 11: \$20 Grocery store gift card. Based on disruptions due to the school year breaks, we will provide an extra \$20 gift card to re-engage the week after a school holiday.

Control arm: BGC after-school program only

1. Children participate in the BGCAs after-school program with CATCH curriculum as described above.
2. At the end of the study, they will receive \$120 as grocery store gift cards.

[figure not shown]

Figure 1. Study design: 2 randomized arms

Outcomes:

- Primary:
 - Child's diet quality: measured by Healthy Eating Index, HEI, scores calculated from the Texas School Physical Activity and Nutrition (SPAN), 2nd Grade.
 - Child's fruits and vegetable consumption, measured by SPAN, 2nd Grade.
- Secondary outcomes:
 - Caregiver/parent diet quality, measured by HEI scores calculated from the SPAN, 8th Grade.
 - Child's physical activity levels
 - Child's body mass index, as percentile of BMI-for-age

Study measurements:

Timepoint measurements for all study participants (child-parent dyads) include:

- baseline (approximately up to 4 weeks prior to the first produce bag and grocery store gift card being distributed). Height and weight will be taken during the first 1-2 weeks of the research program start date during a BGCAA field day.
- mid-point (planned for approximately weeks 5-8)
- end-point (approximately between weeks 16 and 21). Height and weight will be taken during the 19th week of the program at the BGCAA's field day.

Outcomes	Tool	Time points	Administration
Child's Diet (primary)	TX SPAN 2 nd grade 2019-2020 – Dietary questions	Baseline, Mid-point, End point	Child, Guardian-reported Structured interview over the phone by RA
	SPAN Healthy Eating Index scores (includes total, healthy, and unhealthy scores)	Baseline, Mid-point, End point	Child, calculated from SPAN
Physical Activity	TX SPAN 2 nd grade 2019-2020 – Physical activity questions	Baseline, End point	Child, guardian-reported Structured interview over the phone by RA
	Physical Activity Questionnaire – Children		

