- a. Interested participants will be called by study staff to screen and share consent and assent information, which is expected to last approximately 15 minutes. Consent and assent will be collected verbally in order to reduce burden on participating families.
- b. After RA obtains consent and assent, if time allows, will also gather baseline data over the phone on the same phone call. If time constraints exist, staff will schedule another time and date for baseline phone measurements (more below).

3. Participating families (parent-child dyads) will then be allocated to study arms as follows:

- a. Dyads with one reference caregiver and one reference child in the BGCAA after-school program will be randomized to one of the two active arms (family support + after-school program, or after-school program only)

Measurements and data collection procedures:

There will be 3 data collection measurements over the course of 19 weeks. These are the baseline, mid-, and end-point measurements. The initial baseline phone call will take approximately an hour (counting consent/assent), while the mid- and end-point measurements will take approximately 45 minutes to an hour. The height and weight measurements will take an additional 5 minutes. In total, participants can expect to spend approximately 4 hours of their time on study-related measurements and data collection.

Data will be collected by members of study staff listed as study team members in UT-RMS. Data collection will only happen with the families that are actively participating and have consented in to the research, not the families participating in BGCAA's regular program and not participating in our research study.

Questionnaire data:

At each measurement, the research associate (RA), blinded to the active study arm of the participants, will gather parent-reported data and child-reported data with parental guidance over the phone as structured interviews. The structured interviews will be done as follows:

1. The RA places the phone call to the reference parent/caregiver.
2. After introducing themselves and the purpose of the call, they will proceed with the questionnaires as shown in Section #4 (e.g., diet, physical activity, demographics). Questionnaires for children will be asked to the parent (guardian-reported) who can confirm answers with the child if they are present and as needed. At the parent's discretion, the child may answer the questions themselves.

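### The primary child diet questionnaire is listed as guardian-reported, yet the parent may let the child answer at any measurement; the respondent should be held constant across the three visits and recorded.

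*Combined protocol and SAP*

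**What the plan says.** Section 4 (Design and Methodology) defines the first primary outcome as "Child's diet quality: measured by Healthy Eating Index, HEI, scores calculated from the Texas School Physical Activity and Nutrition (SPAN), 2nd Grade". The second, the child's fruit and vegetable consumption, comes from the same questionnaire. The outcomes table in that section describes its administration as "Child, Guardian-reported Structured interview over the phone by RA" and makes no provision for the child to answer.

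Section 11 (Procedure Description, Questionnaire data) covers all three measurements. It says that the RA "will gather parent-reported data and child-reported data with parental guidance over the phone as structured interviews". The RA phones the reference caregiver and puts the child questionnaires to that caregiver, who may check answers with the child if the child is there. The next sentence makes an exception: if the parent so decides, "the child may answer the questions themselves". It is not limited to any visit, any age or any questionnaire.

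On blinding, Section 4 says "Participant and other staff are unblinded". On sequence, Section 11 describes consent and the baseline call and then states "Participating families (parent-child dyads) will then be allocated to study arms as follows". Section 5 (Data Analysis) fits mixed linear models to trajectories from baseline to mid-point and end-point, with time by treatment, time by SNAP and their three-way interaction. Who answered does not appear in the model. No section requires the same respondent at each visit or says that the respondent will be recorded.

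**The concern.** Sections 4 and 11 disagree on who reports the primary outcome. The difference matters because the target of the analysis is change within a child. If a caregiver answers at one call and the child at another, a difference between reporters is read as a change in diet. The children are in grades 1 to 5, about 6 to 11 years old, so the two reports cannot be assumed interchangeable.

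There are two possible consequences. If switching is unrelated to arm, it adds noise to each child's trajectory and costs power. If the share of child respondents at follow-up differs between arms, the arm contrast absorbs part of the reporter difference. Blinding the RA does not prevent the second, because the parent makes the choice, knows the allocation and chooses after it. Maximum likelihood estimation deals with missing visits, not with a change of reporter.

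The documents also suggest how switching could arise. The child speaks to staff for assent (Section 21), and baseline data may be taken on that same call. At later calls the child may or may not be present.

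**Working it through.** **Passages side by side.** Section 4 table: guardian-reported. Section 11 default: caregiver answers, child may confirm. Section 11 exception: child answers if the parent prefers. The table and the default agree; the exception conflicts with the table. Section 5 neither uses nor adjusts for the respondent.

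**Is there a plan figure to reproduce?** There is none for respondent switching. The yardstick used here is the targeted effect of 0.47 at 80% power and alpha 0.05 (Section 15; two-sided assumed). The stated 120 per arm is not needed below. It does not follow from 0.47 alone: 2 × (2.802/0.47)² = 71.1, or 72 per arm without clustering, so 120 implies a design effect of about 1.69 from a cluster size that is not given. That is a separate matter.

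**Bias if the arms differ.** Bias = (difference between arms in share of child reporters at the end-point) × (mean offset between child and parent reports). Both inputs are assumptions.
- Low: 0.10 × 0.25 SD = 0.025 SD; 0.025/0.47 = 5%.
- High: 0.20 × 0.50 SD = 0.10 SD; 0.10/0.47 = 21%.

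The standard error that gives 80% power at 0.47 is 0.47/2.802 = 0.168. With no true effect, a bias of 0.025 SD moves the two-sided type I error from 0.050 to about 0.053, and a bias of 0.10 SD moves it to about 0.092. The direction of any bias is unknown.

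**Noise if the arms do not differ.** Added relative variance of change = p·b²/[2(1−ρ)], where p is the share of children who switch, b the offset and ρ the correlation between visits. All three are assumptions.
- Low: 0.20 × 0.25²/(2 × 0.6) = 0.0125/1.2 = 1.0%.
- High: 0.30 × 0.50²/(2 × 0.4) = 0.075/0.8 = 9.4%.

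Power = Φ(2.802/√(1 + added) − 1.960), which falls from 80% to 79.6% and 76.4% respectively. The formula treats switches as balanced in direction. If all go one way, p becomes p(1−p): 0.16 × 0.0625/1.2 = 0.8% and 0.21 × 0.25/0.8 = 6.6%.

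**Sensitivity to the noise model.** The formula above counts only a mean offset. Suppose instead that switching also lowers the correlation between visits to a fraction k of ρ. The variance factor is then [(1−f)·2(1−ρ) + f·2(1−ρk)]/[2(1−ρ)], with f the share switching.
- ρ = 0.5, k = 0.7, f = 0.10: 1.03, power 79%.
- ρ = 0.7, k = 0.3, f = 0.40: 1.65, power 59%.

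The gap between the two noise models shows that nothing in the documents anchors the size.

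**The case against.** The strongest reply is that the reporter is already mostly fixed. The RA calls the reference caregiver, the questions go to the caregiver, and child answers are an exception given with parental guidance. That is not a swap between two independent informants, so both the rate of switching and the offset could be small. This stands, and it limits the size of the concern.

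A second reply is that no input to the arithmetic comes from the documents. This also stands. A gap of 20 points would mean, for example, 10% against 30% child reporters, a threefold difference in an exceptional practice. A reader might infer that the tip sheets and goal sheets sent only to intervention families lead their caregivers to choose differently. No section links those materials to who answers the interview. What the text supports is narrower: the choice is made after allocation by someone who knows it.

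Third, the interview script and data forms are uploaded separately and are not part of the text reviewed, so a respondent field may already exist. That is possible. It would meet the recording part of the point but would not resolve the conflict between Sections 4 and 11.

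Fourth, fixing the caregiver leaves all primary data with an unblinded reporter, and children eat snacks after school away from the caregiver, so a child's answers may carry information. This is a real trade-off. It is an argument about which respondent to choose, not for letting the respondent vary.

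**Conclusion.** The point holds as a worthwhile and inexpensive correction. Two sections disagree on who reports the primary outcome, and the rule in Section 11 lets the reporter vary within a child after allocation, with nothing in the visible plan to hold it constant, record it or account for it.

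Its size is unknown. The 5 to 21% of the targeted effect and the 1 to 9% added variance are illustrations that rest on an assumed offset of 0.25 to 0.5 SD, an assumed arm difference of 10 to 20 points, assumed switching in 20 to 30% of children and an assumed correlation of 0.4 to 0.6.

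A reader might go further and infer that the arm contrast is biased, or that power will fall towards 59%. The documents support neither: differential switching is possible but not shown, and the larger power loss needs 40% of children to switch together with a steep fall in correlation. A reader might also take the Section 4 table to say that the child only confirms. It does not; that provision is in Section 11.

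**What to change.** Reconcile Sections 4 and 11. For the primary diet items, delete the sentence that gives the parent discretion, so that the same reference caregiver answers at baseline, mid-point and end-point and the child may only confirm answers, as the Section 11 default already allows.

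Add a REDCap field for the actual respondent at each call, and report respondent by arm and visit. If departures occur, run a sensitivity analysis in all randomised children with respondent as a time-varying term. Label it as a sensitivity analysis, because respondent at follow-up is a post-randomisation variable. Do not restrict the analysis to children with the same respondent throughout, since that selects on the same post-randomisation variable.

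The cost is one sentence in the script, one data field and some rescheduled calls when the caregiver is not free. Reporting bias from the unblinded caregiver remains. The change should be made before data collection, because an unrecorded respondent cannot be reliably recovered later.
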